6.1.2 Dosing at Home

Following Visit 1, patients will self-administer their daily morning and evening doses at home at approximately the same times, approximately 12 hours apart, each day for the duration of the study, except for specific clinic visit days when patients will have their doses administered in the clinic.

Prior to Dosing at Home

- Patients in the maintenance LAMA or LABA stratum should take their maintenance LAMA or LABA (and ICS, if applicable) prior to taking blinded study medication.

Blinded Study Medication Administration

- Each patient will follow the Nebulizer Set-Up instructions and blinded study medication label to prepare and self-administer the blinded study medication by inhalation using the reusable study supplied nebulizer attached to the study supplied compressor.
- Blinded study medication nebulization time should be approximately 5 minutes and may not exceed 10 minutes.
- The end time of blinded study medication nebulization is considered to be when a slight sputtering sound from the nebulizer is heard. This will be considered Time 0 for the purposes of scheduling all post-dose study procedures.

- On the evening Prior to the Week 6, Week 12, and Week 24 Visits (or Early Term/Withdrawal visits where 12-hour spirometry will be performed): On a patient paper diary, the patient will record the date, the start time of nebulization, and the end time of nebulization for the evening dose of blinded study medication.

Used Blinded Study Medication

- Patients will be instructed to discard all used ampules of blinded study medication and the open foil pouches that contained the used ampules at home.

Unused Blinded Study Medication

- Patients should be instructed to bring all unused blinded study medication to the clinic at each clinic visit for collection and assessment of medication compliance by the unblinded site staff member.
- If a foil pouch is opened but the blinded study medication is not opened/not used, the patient should seal the opened foil pouch (eg. tape) before returning it to the clinic.

6.2 Investigational Product/Blinded Study Medication

Investigational product/blinded study medication is described in Table 5.

Table 5: Investigational Product/Blinded Study Medication Details

Name:	Ensifentrine	Placebo
Dosage Formulation:	Nebulizer suspension	Nebulizer solution
Unit Dose:	3 mg	0 mg
Concentration (mg/mL)	1.2 mg/mL	0 mg/mL
Route of Administration	Inhalation	Inhalation
Dosing Instructions:	1 ampule (2.5 mL) per dose	1 ampule (2.5 mL) per dose
Manufacturer	The Ritedose Corporation, Columbia, SC, USA	The Ritedose Corporation, Columbia, SC, USA

The ensifentrine formulation is a sterile suspension of micronized ensifentrine in [REDACTED] and supplied as a 2.5 mL nominal fill in single unit-dose low density polyethylene (LDPE) translucent ampule overwrapped in a foil pouch.

The placebo is the same as the ensifentrine suspension except that the active ensifentrine ingredient is omitted, [REDACTED] and is also supplied as a single unit-dose LDPE translucent ampule overwrapped in a foil pouch.

Both ensifentrine and placebo are manufactured using aseptic manufacturing techniques in accordance with Good Manufacturing Practice guidelines and will be provided to the sites as patient kits.

6.2.1 Blinded Study Medication Dispensing and Formulation Information

Patients will be dispensed blinded study medication kit(s) as per the schedule outlined in the SoA with one exception. If a patient is unable to attend a scheduled visit due to disaster, the instructions for blinded study medication dispensing as outlined in Section 8.6 should be followed.

The blinded study medication formulation constituent and concentrations are described in Table 6.

Table 6: [Redacted]

Constituent	Concentration (mg/mL)
[Redacted]	[Redacted]
[Redacted]	[Redacted]
[Redacted]	[Redacted]
[Redacted]	[Redacted]
[Redacted]	[Redacted]
[Redacted]	[Redacted]
[Redacted]	[Redacted]
[Redacted]	[Redacted]
[Redacted]	[Redacted]

6.2.2 Medical Devices

1. No Sponsor manufactured medical device is used in this study.
2. Other medical devices provided for use in this study are:
 - PARI LC Sprint nebulizer
 - PARI Vios PRO Aerosol Delivery System, PARI BOY compressor or equivalent
3. Instructions for medical device use are provided in the package insert.
4. Information on medical device incidents and reporting is provided in Section 8.7.8.

6.3 Preparation/Handling/Storage/Accountability

1. Blinded study medication should be stored below 25°C (77°F) and should not be frozen.
2. An investigator or designee must confirm appropriate temperature conditions have been maintained during transit for all blinded study medication received and any discrepancies are reported and resolved before use of the blinded study medication.

3. All blinded study medication must be stored in a secure, environmentally controlled, and monitored (manual or automated) area in accordance with the labeled storage conditions with access limited to the Investigator and authorized study center staff.
4. The temperature should be monitored, and logs maintained in areas where blinded study medication is stored. If temperature conditions have been compromised or any blinded study medication has not been stored appropriately, this should be documented, and the blinded study medication quarantined until the Sponsor has been notified and confirmed whether it may be used.
5. Only patients meeting the Randomization Criteria in the study may receive blinded study medication and only authorized study center staff may supply or administer blinded study medication.
6. The Investigator, institution, or the head of the medical institution (where applicable) is responsible for blinded study medication accountability, reconciliation, and record maintenance (i.e. receipt, reconciliation, and final disposition records).
7. Further guidance and information for the final disposition of unused blinded study medication are provided in the Pharmacy Manual.

The Investigator, a member of the study center staff, the site pharmacist, or pharmacy team member must maintain an adequate record of the receipt and distribution of all blinded study medication using the Drug Accountability Form. These forms must be available for inspection at any time.

6.4 Measures to Minimize Bias: Randomization and Blinding

1. Both ensifentrine and placebo pouches and packaging are identical in appearance.
2. Packaging of both ensifentrine and placebo will have a blinded description applied and all packs will have a unique kit number applied for identification.
3. Deliveries of both ensifentrine and placebo will not indicate the actual product but will instead indicate a blinded description.
4. Patients will be randomized to receive either ensifentrine or placebo using an electronic Interactive Response Technology (IRT). The IRT will not indicate the treatment arm during the randomization process but will indicate the unique kit numbers to be dispensed to the patient.
5. Site staff (both blinded and unblinded) will only have access to blinded reports within the IRT.
6. An unblinded site staff member not associated with study conduct will administer in-clinic doses.
7. If more than one patient will be at the clinic at the same time, they will be shielded from each other to prevent cross-contamination or observance of treatment.

Note: Patients may be aware of the appearance when pouring blinded study medication into the nebulizer. Therefore, they should be instructed not to inform site personnel of the appearance of their blinded study medication. Similarly, study personnel are not to discuss the appearance with patients or other site personnel. Patients will be instructed to return unused blinded study medication (ie, unopened or unused blinded study medication in taped foil pouches) only to the unblinded site staff at their next visit. The investigator

will need to confirm and document that the blinding procedures have/have not been maintained for each patient throughout the study. See Data Quality Assurance in Section 11.2.

6.5 Emergency Unblinding

The blind will be broken only if specific emergency treatment would require knowing the treatment status of the patient. If the blind needs to be broken, the Investigator will contact the Sponsor or Medical Monitor as soon as feasible. The Investigator may unblind the blinded study medication immediately if he/she feels it is necessary prior to contacting the Sponsor or Medical Monitor. However, the Investigator should promptly document and explain any premature unblinding to the Sponsor and Medical Monitor. Otherwise, all blinding will be maintained until all queries are resolved and the database is locked.

Unblinding that occurs for any other reason, including unintentional unblinding, will be documented and promptly reported to the Sponsor and Medical Monitor.

6.6 Blinded Study Medication Compliance

The prescribed dosage, timing, and mode of administration may not be changed. Any departures from the intended regimen must be recorded in the eCRFs.

At each visit, prior to dispensing blinded study medication, previously dispensed unused blinded study medication (ie, unopened or unused blinded study medication in taped foil pouches) will be retrieved by the unblinded site staff member and compliance assessed. Patients exhibiting poor compliance as assessed by the number of ampule/foil pouch counts dispensed and returned should be counseled on the importance of good compliance to the study dosing regimen and this counseling should be documented in the patient source document.

Noncompliance is defined as taking less than 70% of blinded study medication during any evaluation period (visit to visit).

6.7 Concomitant Therapy

The Medical Monitor should be contacted if there are any questions regarding concomitant or prior therapy.

6.7.1 Rescue Medication

Study albuterol/salbutamol should be used for rescue use. If study rescue albuterol/salbutamol cannot be dispensed at a scheduled clinic visit, the medication may be dispensed alternatively according to local requirements (See Section 8.6). If at any

time during the study albuterol/salbutamol is unavailable in a given country or region, the Medical Monitor must be contacted to discuss and approve alternative rescue medication (See Section 8.6).

6.7.1.1 Documentation of Rescue Medication Use

- Documentation of albuterol/salbutamol during the 3 months prior to Screening should be recorded on the concomitant medication page of the eCRF along with reason for use, dates of administration (start and end dates), and dosing information (dose and frequency). End date should be documented as “Ongoing.”
- Rescue albuterol/salbutamol used during clinic visits where spirometry will be conducted should be recorded in a module provided in the eCRF for each specific spirometry visit. Details (eg, dose (number of puffs), date, and time of administration) will be recorded.
- Rescue albuterol/salbutamol used at all other times after Screening will be documented in the eDiary (eg, number of puffs per day).
- After Screening, use of Rescue Medication will not be recorded in the concomitant medication page of the eCRF.

6.7.2 Permitted Rescue and Background Medications

Permitted rescue and background medications are provided in Table 7.

Any vaccine that is recommended by the patient’s healthcare provider is permitted during the study (e.g. COVID, influenza, pneumonia), and should be recorded in the eCRF.

Table 7: Permitted Rescue and Background Medications

Medication	Condition
Albuterol/salbutamol	Used as rescue medication as needed during the study. Must be withheld for at least 4 hours prior to spirometry. ¹ Should be withheld for at least 4 hours prior to ECGs.
Either LAMA or LABA	Patients entering the study on a maintenance regimen of either LAMA or LABA therapy will be required to remain on that regimen at a stable dose for the duration of the study. Dual LAMA/LABA therapy is not allowed. Stable ICS use is allowed along with a LAMA or LABA maintenance regimen if it was initiated at least 4 weeks prior to Screening. ICS monotherapy is not allowed. Must withhold prior to spirometry: Twice-Daily maintenance LAMA or LABA (or LAMA/ICS or LABA/ICS) for 24 hours and Once-Daily maintenance LAMA or LABA (or LAMA/ICS or LABA/ICS) for 48 hours, including at Visit 1. ¹ The maintenance LAMA or LABA (or LAMA/ICS or LABA/ICS) therapy should resume once all spirometry for a given visit has been completed.
No maintenance or background therapy	Patients entering the study on no maintenance background therapy will not be allowed to initiate background maintenance therapy for COPD (ie, maintenance LAMA or LABA therapy, or ICS therapy) for the duration of the study.
Inhaled corticosteroids (ICS)	Stable use of ICS is permitted IF the patient has been taking the ICS at least 4 weeks prior to Screening (Visit 0) AND the patient is also taking maintenance LABA or LAMA. ICS should not be initiated or discontinued during the study. ICS monotherapy and high dose ICS (e.g. >1000 mcg of fluticasone propionate or equivalent) is not allowed.
¹ If the withholding periods are not met the visit should be rescheduled to be held within 3 days of the scheduled visit. Abbreviations: COPD=chronic obstructive pulmonary disease; LAMA= long-acting muscarinic antagonist; LABA= long-acting β 2 agonist	

6.7.3 Prohibited Medications/Therapy

Prohibited medications and therapies are provided in Table 8.

Table 8: Prohibited Medications/Therapy

Medication	Time Interval
Oral, Systemic or Parenteral Steroid Therapies	3 months prior to Screening Visit and prohibited during the study. ¹
Antibiotics for lower respiratory tract infection	6 weeks prior to Screening Visit and prohibited during the study. ¹ Chronic use of antibiotics is not allowed 6 weeks prior to or during the study.
Inhaled Corticosteroids (ICS) (e.g. ICS monotherapy and patients in the no maintenance therapy stratum) High dose ICS (e.g. >1000 mcg of fluticasone propionate or equivalent)	4 weeks prior to Screening Visit and prohibited during the study.
Oral leukotriene inhibitors (i.e. montelukast, zafirlukast, zileuton)	48 hours prior to Screening Visit and prohibited during the study.
Theophylline and PDE4 inhibitor (e.g. roflumilast, apremilast, crisaborole)	48 hours prior to Screening Visit and prohibited during the study.
Terbutaline	1-day prior to Screening Visit and prohibited during the study.
Ipratropium (including combinations with albuterol/salbutamol)	6 hours prior to Screening Visit and prohibited during the study.
LAMA/LABA combination products	4 weeks prior to Screening Visit and prohibited during the study.
Nebulized LAMA or LABA or ICS For patients in the no maintenance therapy stratum: For patients in the LAMA or LABA stratum:	4 weeks prior to Screening Visit and prohibited during the study. 1-week prior to Screening Visit and prohibited during the study (e.g. patient should switch from nebulized to dry powder or metered dose therapy)
LAMA Excluded ONLY for patients in the no maintenance therapy stratum	4 weeks prior to Screening Visit and prohibited during the study. ²
LABA Excluded ONLY for patients in the no maintenance therapy stratum	4 weeks prior to Screening Visit and prohibited during the study. ²
Oral beta ₂ -agonists	1-week prior to Screening Visit and prohibited during the study.

¹Except for the treatment of COPD exacerbations during the study (Section 11.6). Localized corticosteroid injections (eg, intra-articular and epidural), intranasal and topical corticosteroids are permitted.
 
²Washout of patients on stable background maintenance LAMA or LABA monotherapy for the sole purpose of study eligibility is not recommended.
 
Abbreviations: COPD=chronic obstructive pulmonary disease; ICS=inhaled corticosteroids; LAMA=long-acting muscarinic antagonist; LABA= long-acting β_2 agonist; PDE4= phosphodiesterase 4
	

6.7.4 Recording Use of Concomitant Medications

6.7.4.1 Recording of Rescue Medication and/or LAMA or LABA Medications, and ICS (if applicable)

- Rescue medication (albuterol/salbutamol) use during the study should be recorded as described in Section 6.7.1.
- Use of LAMA or LABA medications, and ICS (if applicable) during the 3 months prior to Screening should be recorded on the concomitant medication page of the eCRF along with reason for use, dates of administration (start and end dates), and dosing information (dose and frequency).
 - For patients in the maintenance LAMA or LABA therapy stratum, the end date for LAMA or LABA, and ICS (if applicable) should be documented as “Ongoing.”
 - For patients not in the maintenance LAMA or LABA therapy stratum, the actual end date should be documented, if applicable.
- For patients in the maintenance LAMA or LABA therapy stratum, the LAMA or LABA (or LAMA/ICS or LABA/ICS) medication used during the study should be recorded in the eDiary only.

6.7.4.2 Recording of Medications other than Rescue Medication and/or LAMA or LABA or ICS Medications

All COPD medications used within 3 months prior to Screening will be recorded in the eCRF. All non-COPD medications will be recorded in the eCRF starting at Screening and changes recorded during the study. Information recorded will include, but may not be limited to items such as:

- Reason for use.
- Dates of administration including start and end dates.
- Dosage information including route, dose, and frequency.

6.8 Treatment After the End of Study

There are no plans to provide post-study treatment, including study medication for compassionate use following study completion.

At the end of the blinded study medication treatment period (Visit 5 or Visit 9 or early termination), patients may resume conventional COPD therapy as prescribed by the investigator or other physician.

Medications initiated after the end of study treatment should not be entered into the eCRF except for those given for a serious adverse event (SAE).

7.0 DISCONTINUATION OF BLINDED STUDY MEDICATION AND PATIENT DISCONTINUATION/WITHDRAWAL

7.1 Discontinuation of Blinded Study Medication

Patients who permanently discontinue blinded study medication are not required to withdraw from the study unless they test positive for COVID-19 active disease. If a patient must permanently discontinue blinded study medication for reason(s) other than testing positive for COVID-19 active disease, the patient should complete the “Patient Discontinuation/Withdrawal from the Study” assessments described in Section 7.3 as soon as possible. In addition, every effort should be made by the investigator/staff to keep the patient in the study to collect important efficacy and safety data as detailed in Section 7.2.

Circumstances potentially requiring or actually resulting in discontinuation of blinded study medication are described below.

See the SoA (Section 1.3) for data to be collected at the time of treatment discontinuation and follow-up and for any further evaluations that need to be completed.

7.1.1 Does Not Meet Criteria for Randomization

If a patient who does not meet the Randomization Criteria is inadvertently randomized and receives blinded study medication, the Medical Monitor must be contacted and will consult with the Sponsor to determine if the patient may continue, must be discontinued from blinded study medication and/or discontinued from the study.

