7.1.7 Other Criteria

Other criteria that may or may not require permanent discontinuation of blinded study medication include but are not limited to adverse event, lack of efficacy, protocol deviation, non-compliance, study closed/terminated, investigator discretion or patient withdrawal of consent.

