7.3 Patient Discontinuation/Withdrawal from the Study

A patient may withdraw from the study at any time at his/her own request, may permanently discontinue blinded study medication but wish to remain in the study, or may be withdrawn from administration of blinded study medication or from all study participation at the discretion of the Investigator at any time for safety, behavioral, compliance, or administrative reasons. See the SoA (Section 1.3) for data to be collected at the time of study discontinuation and follow-up and for any further evaluations that need to be completed.

- If the patient withdraws consent for disclosure of future information, the Sponsor may retain and continue to use any data collected before such a withdrawal of consent.
- If a patient withdraws from the study, he/she may request destruction of any samples taken and not tested, and the Investigator must document this in the study center study records.

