9.3 Populations for Analyses

mITT population: will include all patients randomized and treated with blinded study medication in the study. Patients will be handled as randomized in the mITT analyses.

PP population: will include all patients in the mITT without any major/important protocol deviations considered to have an impact on efficacy assessments. Reasons for exclusion will be specified at a Blind Data Review Meeting prior to database lock (DBL) and may include violations of inclusion/exclusion criteria, violations of withdrawal criteria, incorrect randomization, use of prohibited medication and non-compliance.

Safety set: will include all patients randomized and treated in the study. Patients will be handled by actual treatment in the safety analyses.

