2.5. ESTIMANDS

The primary and secondary estimands to support regulatory decisions are described in Table 1.

[REDACTED]	[REDACTED]	[REDACTED]	[REDACTED]
[REDACTED]	[REDACTED]	[REDACTED]	[REDACTED]
[REDACTED]	[REDACTED]	[REDACTED]	[REDACTED]
[REDACTED]	[REDACTED]	[REDACTED]	[REDACTED]

Table 1: List of Estimands

Estimand	Definition	Attributes			
		Population	Variable/ Endpoint	Intercurrent event handling strategy	Population-level summary measure
Primary	The efficacy of ensifentrine on lung function compared to placebo over a 12-hour dosing interval in patients with moderate to severe COPD.	Patients with moderate to severe COPD aged 40-80 years (inclusive) that are in the modified intent-to-treat (mITT) population. See full list of inclusion and exclusion criteria in Sections 5.1, 5.2 and 5.3 of study protocol.	Change from baseline forced expiratory volume in 1 second (FEV ₁) to average FEV ₁ area under the curve over 12 hours (AUC _{0-12h}) at Week 12.	Regardless of whether the patient discontinues treatment prematurely and regardless of major protocol deviation, as per the Treatment Policy strategy.	Estimated treatment difference at Week 12 of the double-blind period (and corresponding 95% confidence interval [CI]) from analysis of covariance (ANCOVA) analysis.
Secondary	To evaluate the effect of ensifentrine on other lung function parameters.	Patients with moderate to severe COPD aged 40-80 years (inclusive) that are in the mITT population. See full list of inclusion and exclusion criteria in Sections 5.1, 5.2 and 5.3 of study protocol.	
 Change from baseline FEV₁ to average FEV₁ AUC_{0-4h} at Week 12 Change from baseline FEV₁ to peak FEV₁ at Week 12 Change from baseline FEV₁ to morning trough FEV₁ at Week 12 	Regardless of whether the patient discontinues treatment prematurely and regardless of major protocol deviation, as per the Treatment Policy strategy.	Estimated treatment difference at Week 12 of the double-blind period (and corresponding 95% CI) from ANCOVA analysis.

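### Sections 7.1.1 and 7.3 allow a consenting, dosed patient to be taken out of the whole study for an eligibility error or non-compliance, against the plan's own retention rule and treatment-policy estimand

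*Protocol*

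**What the plan says.** **Rules that allow removal.** Protocol 7.1.1 covers a patient who fails the Randomization Criteria but is randomised and dosed. The Medical Monitor consults the Sponsor, and the outcome is either that the patient continues or that the patient "must be discontinued from blinded study medication and/or discontinued from the study". The rule is wide, because the fifth exclusion in Protocol 5.3 makes any failed inclusion or exclusion criterion a failure of the Randomization Criteria. Protocol 7.3 allows a patient to be withdrawn from study drug alone, or "from all study participation at the discretion of the Investigator at any time for safety, behavioral, compliance, or administrative reasons". Protocol 6.6 sets non-compliance at under 70% of study medication in any one interval between visits.

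**Rules that point to retention.** Protocol 7.1, the parent of 7.1.1, says that "every effort should be made by the investigator/staff to keep the patient in the study to collect important efficacy and safety data". Protocol 7.2 repeats that stopping drug does not oblige a patient to leave the study, active COVID-19 excepted, and sets out full visits as the ideal with three reduced options. Protocol 7.1.7 lists "adverse event, lack of efficacy, protocol deviation, non-compliance, study closed/terminated, investigator discretion or patient withdrawal of consent" as criteria that may or may not call for stopping drug; withdrawal of consent is a separate item from deviation and non-compliance.

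**What the analysis needs.** The mITT population "will include all patients randomized and treated with blinded study medication in the study" (Protocol 9.3; SAP 5.5 is the same apart from the excluded sites). For the primary and key secondary estimands, SAP 2.5 handles intercurrent events thus: "Regardless of whether the patient discontinues treatment prematurely and regardless of major protocol deviation, as per the Treatment Policy strategy".

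**The concern.** A treatment-policy estimand needs the outcome at the scheduled time from every patient in the population, on drug or off it. A patient dosed despite an eligibility error, or taking too little drug, is in that population. Ending that patient's participation does not take the patient out of the analysis. It replaces an outcome that could have been measured with an early-termination value or an imputed one.

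The loss would follow from study decisions tied to eligibility and adherence, in patients who may be willing to keep attending. It also serves no analytic purpose, because Protocol 9.3 and SAP 5.7 already allow such patients to be left out of the per-protocol population. At stake are the Week 12 spirometry endpoints and, with less protection, Week 24 E-RS and SGRQ, which stand third and fourth in the testing order (SAP 7.4).

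**Working it through.** **Step 1. Set the rules side by side.**

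| Question | 7.1.1 and 7.3 | 7.1, 7.2 and SAP 2.5 |
|---|---|---|
| Can follow-up end while the patient still consents? | Yes, after an eligibility error (7.1.1) or for compliance or administrative reasons (7.3) | Retain the patient; only active COVID-19 is named as forcing exit |
| Does the patient stay in the primary analysis? | Not addressed | Yes, whatever deviation occurred |

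The two columns can both be followed only if the discretion to remove is never used. That is the inconsistency.

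**Step 2. Follow a removed patient into the analysis.**

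- *Removed before Week 12.* Protocol 7.3.1.1 asks for 12-hour spirometry at the early-termination visit, on drug where possible. SAP 6.4 uses that curve whenever it was taken. If drug then stops, an early on-drug value stands in for the Week 12 treatment-policy value. For a patient already off drug, the spirometry is optional.
- *No usable curve.* SAP 16.1.2 imputes under missing at random from treatment, region, the two strata, baseline FEV₁ and Week 12 AUC₀₋₁₂ₕ. No term marks a patient as off drug, non-compliant or ineligible.
- *Removed between Week 12 and Week 24.* The primary value normally exists, but E-RS and SGRQ at Week 24 do not, and the 12-hour spirometry request does nothing for them.

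**Step 3. Reproduce the plan's power.** Inputs from Protocol 9.2: SD 250 mL, 500 vs 300 evaluable, two-sided 5%, difference 59 mL.

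SE = 250 × √(1/500 + 1/300) = 18.26 mL

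Power = Φ(59/18.26 − 1.96) = Φ(1.27) = 89.8%, against 90% stated. The figure reproduces. All 800 randomised patients are counted as evaluable, so there is no dropout allowance.

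**Step 4. Illustrate the size.** The documents do not give the share removed. Assume a share m is lost equally from both arms, with no curve recovered and nothing gained from imputation. For the shift in the estimate, assume also that imputation credits these patients with the full 59 mL when the true effect in them is nil, so shift = m × 59 mL.

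| m (assumed) | Patients | n per arm | SE (mL) | Power | Shift (mL) |
|---|---|---|---|---|---|
| 1% | 8 | 495 vs 297 | 18.35 | 89.5% | 0.6 |
| 2% | 16 | 490 vs 294 | 18.44 | 89.2% | 1.2 |
| 5% | 40 | 475 vs 285 | 18.73 | 88.3% | 3.0 |

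At 5% the power loss is 89.8 − 88.3 = 1.5 points, and the shift is 3.0/18.26 = 0.16 of a standard error.

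**The case against.** The strongest reply is that the plan mandates nothing. Section 7.1.1 is a case-by-case consultation in which continuing is one outcome. It sits under a section that asks for retention. Poor compliance leads first to counselling (6.6), and 7.3 offers stopping drug alone as an alternative. This stands: a reader might infer that the plan will generate missing data, but the text only allows it.

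The reply also points to the safeguards. Early-termination curves enter the primary analysis, and patients removed after Week 12 normally already have their primary value. SAP 16.1.2 adds opposite-arm average imputation, which penalises ensifentrine, and a tipping-point analysis. These limit the damage and show how far a conclusion depends on missing values. They cannot recover an outcome from a patient who would have attended.

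A reader might further infer a bias in favour of ensifentrine. That is plausible for poor compliers, but the documents do not establish it. The data feeding the imputation include off-treatment and end-of-study values (SAP 7.3). Failing a criterion such as diary completion says nothing in itself about response. The shift in Step 4 needs an assumed removal rate, no usable curve and no drug effect in any removed patient, none of which the documents supply.

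Finally, a blanket repair would cause trouble. A positive COVID-19 result before randomisation is itself a randomisation exclusion (5.3), and active infection requires study withdrawal (7.1.6). Administrative grounds can include site or study closure, which Appendix 2 permits. The reduced options in 7.2 do not secure every endpoint: 7.2.2 has no Week 12 clinic visit, 7.2.3 is by phone only, and none of the three lists E-RS. All of this stands and narrows the fix.

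**Conclusion.** The point holds as a mismatch between data collection and estimand. Sections 7.1.1 and 7.3 permit the follow-up of a consenting, dosed patient to end for reasons that the estimand says should not matter, and this conflicts with the retention rule in 7.1 and 7.2. Some avoidable missing Week 12 and Week 24 data are therefore allowed.

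The number affected is not given and is probably small. On an assumed 1 to 5% loss with nothing recovered, power stays at 88.3% or above. A shift of 0.6 to 3.0 mL follows only if all the Step 4 assumptions hold together, so it illustrates scale and is not an estimate of bias. The documents do not support reading this as a material loss of power or as a demonstrated advantage to the drug. The case for change is that the loss is preventable at source and cheap to prevent.

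**What to change.** **Section 7.1.1.** State that an eligibility error alone does not end study participation. If study drug is stopped, the patient is followed under 7.2, preferably with full scheduled visits. The exceptions are withdrawal of consent, a safety reason, and the existing COVID-19 withdrawal rule in 7.1.6.

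**Section 7.3.** Remove compliance as a ground for ending all participation of a patient who still consents, and route such patients to 7.2. Limit the administrative ground to closure of the site or the study. Leave the safety and behavioral grounds as they are.

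Whether a patient stays on study drug remains the existing clinical decision and is not touched by this change. Full visits are preferred because the reduced options would leave gaps in the Week 12 curve, in E-RS or in both.

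The cost is two wording changes and a few additional follow-up contacts or visits.
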